Primary objective	To evaluate the impact of LLINs treated with a pyrethroid insecticide plus pyriproxyfen (PPF LLINs), as compared to LLINs treated with a pyrethroid plus piperonyl butoxide (PBO LLINs), on malaria incidence in Uganda. We will test the hypothesis that malaria incidence will be lower in intervention clusters (randomised to receive PPF LLINs) than in control clusters (randomised to receive PBO LLINs).
Secondary objectives	
 1 To evaluate the impact of PPF LLINs vs PBO LLINs on parasite prevalence, anaemia and vector density (subject to available funding) 2 To estimate the cost-effectiveness of delivering PPF LLINs, as compared to PBO LLINs 3 To assess net durability, survivorship and use of PPF LLINs vs PBO LLINs (funding permitting) 4 To evaluate the impact of the COVID-19 pandemic on malaria burden and care in Uganda
Study site	With the Ministry of Health, we have established a high-quality malaria surveillance programme. Health facilities selected for our malaria surveillance network are referred to as Malaria Reference Centers (MRCs). For this study, a cluster has been defined as the target area of an MRC (the village where the MRC is located, and adjacent villages where care-seeking at the MRC is expected to be high). The study will be conducted in 64 clusters within 32 districts in Uganda, covering a wide range of settings with high malaria burden.
Cluster randomisation	The MRCs will be the focal point of the clusters (32 districts x 2 MRCs per district = 64 clusters). Clusters have been randomised in blocks of 2 to receive PPF LLINs (intervention) or PBO LLINs (control), with two sub-counties in each district receiving one of the LLIN types in a 1:1 ratio.
Intervention	A universal LLIN distribution campaign will be led by the National Malaria Control Division and partners. LLINs will be distributed to the sub-county surrounding each cluster.
Evaluation methods & sample size	
1) Health facility surveillance. Our malaria surveillance programme supports training in data management and high-quality laboratory testing (microscopy or rapid diagnostic tests) on all patients with suspected malaria. Using this surveillance system, we have developed a method to estimate the incidence of malaria in target areas around the MRCs, providing a direct measure of the burden of malaria. For all patients presenting to the MRCs, information on the location of their residence will be collected. Estimates of malaria incidence will be calculated by dividing the number of laboratory-confirmed malaria cases diagnosed at each MRC (among patients residing in the target area per unit time) by the total population of the MRC target area. To evaluate the impact of the intervention, we will estimate malaria incidence at the MRCs for the 24 months after LLIN distribution.
 
2) Enumeration and census surveys. To estimate the population of the MRC target areas, and to generate a sampling frame for the first community survey (to be carried out 12 months after LLIN distribution), we will enumerate and map all households within each MRC target area. To derive a more accurate estimate of the population of the MRC target areas, we will conduct a census survey of the MRC target areas, concurrently with the first cross-sectional survey.
 
3) Cross-sectional community surveys. Shortly after LLIN distribution (in selected clusters) and at 12 and 24 months following LLIN distribution, randomly selected households will be surveyed from each of the 64 clusters. The survey will include a household questionnaire and clinical & laboratory evaluation of children aged 2-10 years. We will survey 50 households in each cluster (n=3,200), aiming to recruit all eligible children in each household (approximately 5,760) per survey. In 32 clusters (one per district), we will enroll residents of all ages from participating households into the clinical survey, to estimate the impact of COVID-19 on malaria during the 12-month survey.
 
4) Entomology surveys. Funding permitting, mosquitoes from 10 randomly selected households in all 64 clusters will be collected using prokopack aspirators to estimate malaria vector density, and to collect samples for monitoring of insecticide resistance. Collections will be carried out alongside the cross-sectional surveys.
 
5) Economic evaluation. Cost-effectiveness will be assessed at the end of the study by collecting cost data for materials and labour and using effectiveness data to estimate the number of malaria cases averted. Incremental cost-effectiveness ratios (USD per disability-adjusted life year averted and per malaria case averted) will be the primary outcomes.
 
6) LLIN survivorship and durability. At 12 and 24 months after distribution of nets, we will quantify net survivorship in the cross-sectional surveys and (if funding is available) will withdraw (and replace) a subset of LLINs to assess durability using standard WHO methodology.

Primary outcome	The primary outcome will be malaria incidence within the total population of the MRC target areas.
Secondary outcomes	
1) Community surveys: In all clusters, prevalence of parasitaemia (in children aged 2-10 years) and prevalence of anaemia (haemoglobin < 11 g/dL in children 2-4 years). In selected clusters (n=32), during the 12-month survey, prevalence of parasitaemia (all ages & stratified by age), and prevalence of antibody responses, suggesting prior exposure to SARS-CoV-2 antigens (COVID-19)
 
2) Entomology surveys: Malaria vector density (if funding is available)
 
3) Economic evaluation: Incremental cost-effectiveness ratios (USD per disability-adjusted life year averted and per malaria case averted)
 
4) LLIN survivorship and durability: Survivorship: prevalence of nets present, and in use; Durability: proportionate hole index (subject to available funding)

Study personnel and institutions

Investigators

[name], MD, PhD, DTM&H

Role in project: Principal investigator

Professor of Malaria & Global Health, London School of Hygiene & Tropical Medicine, UK

Infectious Diseases Research Collaboration, Kampala, Uganda

Email: [contact]

[name], MBChB, MPH, PhD

Role in project: Co-PI, Uganda site investigator

Professor, Department of Medicine, Makerere University, Kampala, Uganda

Executive Director, Infectious Diseases Research Collaboration, Kampala, Uganda

Email: [contact]

[name], MD, PhD

Role in project: Co-investigator

Professor, Department of Medicine, University of California, San Francisco, USA

Infectious Diseases Research Collaboration, Kampala, Uganda

Email: [contact]

[name], MBChB, MSc, PhD

Role in the project: Co-investigator

Lecturer, Department of Medicine, Makerere University, Kampala, Uganda

Epidemiologist, Infectious Diseases Research Collaboration, Kampala, Uganda

Email: [contact]

[name], MBChB, MSc

Role in the project: Co-investigator

National Malaria Control Division, Uganda Ministry of Health, Kampala, Uganda

Infectious Diseases Research Collaboration, Kampala, Uganda

Email: [contact]

[name], MA, MSc, PhD, FRES

Role in project: Co-investigator

Professor of Evolutionary Genetics, Liverpool School of Tropical Medicine, UK

Email: [contact]

[name], MD, MA

Role on project: Co-investigator

Associate Professor, Department of Medicine, University of California, San Francisco, USA

Email: [contact]

[name], MD

Role on project: Co-investigator

1.1 Introduction

Over the last 15 years, malaria control interventions have been scaled-up dramatically across Africa, resulting in an estimated 40% decrease in the incidence of disease due to *P. falciparum* between 2000 and 2015 [1]. However, despite these encouraging trends, decreases in the burden of malaria have not been uniform across Africa and have been slowest in countries with the highest burden, such as Uganda. Uganda is emblematic of high-burden countries in sub-Saharan Africa; it reported the third highest estimated number of malaria cases in 2018, representing 5% of the global malaria case burden [2]. Malaria transmission occurs throughout the year in 95% of the country, with *P. falciparum* responsible for 90-98% of infections [3]. The most common malaria vectors are *Anopheles gambiae* s.s., *A. arabiensis*, and *A. funestus*; *A. gambiae* s.s. is the dominant species in most areas [4]. Since 2014, Uganda has embarked on the Uganda Malaria Reduction Strategic Plan, an ambitious program to reduce malaria mortality to near zero, morbidity to 30 cases per 1000 per year, and malaria parasite prevalence to less than 7%, by 2020 [5]. However, a review of Uganda's malaria programme from 2014 to 2019, conducted by the Ministry of Health (MOH), provided a mixed picture on progress [6]. From 2014 to 2019, in-patient malaria deaths declined from 17 to 9 deaths per 100,000 population, but did not meet the target of 5 deaths per 100,000. During that five-year period, the incidence of total malaria cases fell from 460 to 282 per 1000 population, but the incidence of confirmed malaria cases increased from 150 to 192 per 1000 population, likely due in part to the expansion of diagnostic testing for malaria. These findings highlight the challenges facing Uganda, and the urgent need for improved strategies to control and ultimately eliminate malaria in the country.

1.2 Malaria control interventions in Uganda

Malaria control in Uganda, like elsewhere in sub-Saharan Africa, has focused primarily on three interventions: case management with artemisinin-based combination therapies (ACTs), long-lasting insecticide treated nets (LLINs), and indoor residual spraying of insecticides (IRS). Over the last decade, Uganda has dramatically increased ACT use and LLIN coverage, and to a lesser extent coverage with IRS [7]. However, evidence of the impact of these interventions on clinical outcomes remains limited. Artemether-lumefantrine (AL) was adopted as first-line therapy for uncomplicated malaria in 2006, replacing older regimens limited by drug resistance, and multiple studies from investigators in our PRISM group have documented that this drug and other ACTs remain highly efficacious [8], with no evidence of artemisinin resistance [9]. Although the increased availability of AL for malaria treatment has likely played a role in reducing malaria-specific mortality [10], little evidence of the impact of effective case management in reducing malaria morbidity in high transmission settings is available.

In addition, the COVID-19 pandemic may also have effects on malaria control through decreased availability of ACTs or rapid diagnostic tests through interruption of the supply chain; likewise, hospital beds may become scarce if communities become overwhelmed by COVID-19 cases. National lockdowns (one of which has already occurred and been lifted in Uganda) or travel restrictions may further affect the public's ability to access health facilities and timely care. For example, the WHO and others predict that if LLIN distribution stops and case management is significantly disrupted, malaria deaths in sub-Saharan Africa could double compared to 2018 [11, 12]. The overlap in symptoms between malaria & COVID-19, particularly fever, may impact on the provision of care for both infections. A thorough understanding of the impact of COVID-19 on malaria burden and care in Uganda is needed.

1.3 LLINs in Uganda

In Uganda, LLINs are the primary tool for malaria prevention, and considerable efforts have been made to achieve universal coverage of LLINs [13]. In 2013-14 Uganda became the first country to deliver LLINs free-of-charge nation-wide, with over 90% of households reporting ownership of at least one LLIN following the mass distribution campaign [14]. Subsequently, Uganda conducted a national Malaria Indicator Survey in 2014-15 which assessed parasite prevalence in children aged 0-59 months. Nationally, parasite prevalence was 19% by microscopy (down from 42% in 2009) and 30% by rapid diagnostic test (down from 55% in 2009) [14]. As part of our PRISM project, we also evaluated the impact of the 2013-14 LLIN distribution campaign using data from intensive cohort studies and entomological surveys at 3 sites with varying transmission intensity, including Walukuba sub-county (Jinja district), Kihiihi sub-county (Kanungu district) and Nagongera sub-county (Tororo district). Surprisingly, although the mass distribution campaign substantially increased LLIN coverage levels, and was temporally associated with an overall decrease in parasite prevalence, we observed little effect on clinical malaria indicators. Only in Kihiihi, where medium-level malaria transmission was documented, did we observe a significant decrease in the incidence of malaria following LLIN distribution [15].

In 2017-18, Uganda conducted a second mass LLIN distribution campaign. Prior to this campaign, our group conducted a large cross-sectional survey of 5,200 households to estimate baseline LLIN coverage levels in 104 health sub-districts located in 48 districts, covering 5 of the 10 regions in the country [16]. Three years after the earlier LLIN campaign, we found that LLIN coverage levels had dropped substantially, with only 65% of houses owning at least one LLIN (down from 94% in 2014), and only 14% of households owning at least one LLIN per two residents (down from 65% in 2014, Figure 1).

In 2017, we also conducted a clinical survey of parasite prevalence in children aged 2-10 years [17]. In total, 5,196 households and 8,834 children with blood smear results were included in the analyses. Overall, parasite prevalence was 26.0%, ranging from 8.0% in the South West to 53.1% in East Central. Limiting the analysis to children 2-4 years of age residing in the five regions, parasite prevalence was 21.4%. Comparisons made between the 2009 and 2014-15 Malaria Indicator Surveys and the 2017 survey (Figure

[figure not shown]

Figure 1. LLIN ownership and coverage from 2014 to 2017
Reduced ownership & coverage 3 years after the LLIN distribution campaign.

[figure not shown]

Figure 2. Change in parasitaemia over time. Parasitaemia in children 2-4 years fell from 46% in 2009 to 17% in 2014, but rose to 21% in 2017.

2) indicated that parasite prevalence fell from 45.6% to 16.9% between 2009 and 2014-15, with significant decreases in all five regions of the country ($p<0.001$ for all comparisons). However, in 2017, prevalence increased in all areas, which was statistically significant in the Mid-Eastern (6.0% vs. 19.1%, $p<0.001$) and Mid-Western regions (19.5% vs. 25.7%, $p=0.02$).

Thus, although the 2013-14 national LLIN distribution campaign successfully reached its target coverage level, we observed a limited effect on clinical malaria indicators and transient reduction in parasite prevalence. Moreover, LLIN coverage dropped substantially after 3 years. These findings highlight the challenges of relying on LLINs as the primary method of vector control in Uganda.

1.4 IRS in Uganda

IRS was adopted as a key component of Uganda's malaria control strategy in 2006. Initial efforts were focused on epidemic-prone areas in the southwestern part of the country.

However, in 2009, the IRS programme was moved to 10 high burden districts in northern Uganda. Initially organochlorine/pyrethroid insecticides were used for IRS, but the insecticide was changed to carbamates in 2010, due to the emergence of resistance to pyrethroids and DDT. The IRS programme in northern Uganda consistently achieved high coverage levels (above 95% of targeted households) and was associated with marked reductions in measures of malaria morbidity [18]. In 2014, the IRS program was withdrawn from the 10 northern districts and relocated to 14 new districts in north-eastern Uganda, with the hope that gains achieved by IRS in the north would be sustained by LLINs distributed after the last cycle of IRS. However, data from our health facility surveillance system showed that measures of malaria morbidity rose sharply within 4 months of the discontinuation of IRS, reaching pre-IRS levels (Figure 3) [19]. These data were instrumental in the decision to conduct one additional round of IRS in northern Uganda in 2017.

The relocation of the IRS programme to north-eastern Uganda in 2014 allowed us to estimate impact of IRS in Nagongera sub-county, Tororo district. Since 2011, we have been following a cohort of households and carrying out entomology surveys through our PRISM project

[figure not shown]

Figure 3. Impact of vector control on malaria test positivity rate in Apac. Monthly trends in malaria test positivity rate (TPR, blue line) in Apac following delivery of multiple rounds of IRS with different insecticides (red, green, yellow bars) and universal distribution of LLINs (light blue bar).

[figure not shown]

Figure 4. Temporal changes in the entomologic and clinical malaria indicators from 2011 to 2017. (4A) Monthly trends in daily human biting rates, annual entomological inoculation rates, and rainfall. (4B) Monthly trends in symptomatic malaria, microscopic parasitaemia, and combined microscopic and sub-microscopic parasitaemia. Blue bars = LLIN distribution, Pink bars = IRS with bendiocarb, Yellow bars = IRS with pirimiphos-methyl (*Nankabirwa, et al, submitted for publication*).

(Program for Resistance, Immunology, Surveillance, and Modelling of Malaria) (Figure 4). Our detailed longitudinal data have shown that repeated rounds of IRS have been temporally associated with dramatic reductions of daily human biting rates (a surrogate for malaria transmission, panel 4a) and malaria incidence (panel 4b). However, despite the overall reductions, malaria metrics increased just prior to each round of IRS, illustrating the fragile nature of the gains achieved.

Moreover, the prevalence of parasitaemia based on a highly sensitive measure (loop-mediated isothermal amplification [LAMP]) remained >10% after each round of IRS, demonstrating a persistent reservoir available to drive a resurgence in malaria transmission and cases, as occurred after IRS was withdrawn in the northern districts [20]. In Nagongera, we also observed a shift from *A. gambiae* s.s. as the primary vector to *A. arabiensis* after the start of IRS, which was also noted after the implementation of IRS in northern Uganda [21]. This shift in mosquito vectors could have important implications on the efficacy of other vector control interventions, such as LLINs, as *A. arabiensis* tends to bite earlier in the evening, and is more likely to feed on domestic animals, and to feed outdoors, than *A. gambiae* s.s. There are plans to continue the IRS program in the 14 districts in north-eastern Uganda. Spraying will be carried out annually using an appropriate chemical rotate at least every 3 years, in accordance with Uganda's Insecticide Resistance Management (IRM) plan for control of malaria vectors in Uganda [22]. There is clear evidence that IRS has had a substantial impact on reducing the burden of malaria in Uganda. However, gains have been fragile, as evidenced by the resurgence of malaria when IRS was withdrawn in northern Uganda, and by the peaks in malaria metrics seen just prior to each round of IRS. New strategies to reduce transmission and sustainably maintain malaria control gains are needed to clear a pathway toward malaria elimination in Uganda.

1.5 Health facility surveillance

In Uganda, the Health Management Information System (HMIS) is the primary source for malaria surveillance data. Aggregate data from all government-run and some private health facilities are assembled and reported at regular intervals using standardised registers and reporting forms. The introduction of the District Health Information System 2 (DHIS2), an electronic form of HMIS, in 2012, improved the collation of data at both the district and national level. DHIS2 is a web-based system with data from paper-based reports submitted to a central database. Despite improvements, concerns remain about the quality of HMIS data due to incomplete reporting, data entry errors, and reporting of malaria cases based on poor quality diagnostics or a lack of laboratory confirmation altogether. In addition, because the HMIS system relies solely on aggregate data, it is not amenable to stratification or subgroup analyses. Consequently, estimates of malaria morbidity may be biased, making it difficult to accurately monitor trends over time and space, or to measure the impact of control interventions. Despite these limitations, HMIS remains the only source of routine malaria surveillance data.

To improve the quality of malaria surveillance data, our group created the Uganda Malaria Surveillance Project (UMSP), in collaboration with the National Malaria Control Division, in 2006. The project initially included 6 health facilities, with individual level data collected electronically from all outpatients. Data are

[figure not shown]

Figure 5. Malaria reference centers in Uganda. In total, 64 malaria reference centers (MRCs) cover 32 districts.

collected on patient demographics, laboratory test results, diagnoses, and treatments prescribed. The project has supported training in data management and high-quality laboratory testing (microscopy or malaria rapid diagnostic tests) on all patients with suspected malaria. In 2014, the programme expanded from 6 to 21 health facilities, and was expanded further to 35 sites in 2018-19. With funding support from the NIH, we expanded to 64 sites in 2020 (Figure 5). Health facilities selected for our malaria surveillance network are referred to as Malaria Reference Centers (MRCs) and provide a wide geographic scope across Uganda. The primary metrics used to monitor trends from our malaria surveillance network have been the number of laboratory confirmed cases of malaria and the test positivity rate (number of confirmed cases of malaria / number of suspected cases undergoing laboratory testing). However, these metrics do not provide a direct measure of the burden of malaria in defined populations at risk. To address this limitation, we have developed a method to estimate the incidence of malaria in target areas around the health facilities.

To accomplish this, we began collecting data on village and parish of residence for all patients presenting to the health facilities in 2017. To generate maps of villages around the MRCs, a preliminary map was made using a list of villages obtained from the government and shape files that are publicly available. The GPS coordinates of each MRC were then verified and the names and shape files for all villages of interest were confirmed. A final clean version of the map was printed and shared with the MRC to help improve the quality of the data collection (Figure 6).

[figure not shown]

Figure 6. Map of Anyeke MRC target area.

Using population estimates for MRC target areas, and assuming all care for malaria within the target areas occurs at the health facility (a reasonable assumption in rural Uganda), we are able to generate estimates of malaria incidence, defined as the number of cases of laboratory confirmed malaria diagnosed at the health facility among patients residing in the target area per unit time / the population of the target area. For the numerator, the total number of malaria episodes from the MRC target area during the time of interest is calculated as the sum of the following: laboratory confirmed malaria cases, plus the estimated number of

[figure not shown]

Figure 7. Estimating malaria incidence at the Anyeke MRC.

Anyekie MRC test positivity rate and malaria incidence by month from April 2019 to March 2020, with incidence estimates calculated using four different sources) to estimate the population of the target area.

cases of suspected malaria with no test results, plus the estimated number of cases of laboratory confirmed malaria cases with missing information on village of residence. For the denominator, four population databases have been consulted, including High Resolution Settlement Layer (HDSL), Uganda Bureau of Statistics (UBOS), the AfriPop project (AFRIPOP), and Oak Ridge National Laboratory's LandScan (LANDSCAN) (Figure 7). In the future, we plan to conduct a census survey of each MRC target area to confirm the population. By establishing the capacity to estimate malaria incidence for the target areas of the MRCs, we have built a platform which will allow us to assess the impact of LLINs distributed through the national LLIN campaign on malaria incidence on a wide scale.

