6.1 Data collection at MRCs

At each MRC, individual-level data from standardised registers for all patients presenting to the outpatient departments are entered into an Access database by on-site data entry officers. Primary data captured comes from the HMIS 002 standardised form (Appendix C) and includes location of residence (parish and village), age, gender, body temperature, history of subjective fever, type of malaria test done (rapid diagnostic test or microscopy), malaria diagnostic test results, any diagnoses given, and any treatments prescribed. The research team supports the sites with training, site support supervision, and buffer stock of laboratory supplies/consumables. We employ full-time regional surveillance coordinators based around the country, each supervising 8-10 MRCs. Team members based in Kampala include the programme manager, several study epidemiologists, a data manager, a laboratory manager, and administrative staff. Members of the core team visit the MRCs on a regular basis to provide refresher training and feedback, and to conduct laboratory quality control procedures. Core team members are also responsible for generating periodic reports, communicating with MOH officials and other key stakeholders, and conducting data analyses.

Table 2. Malaria reference centers

	District	MRC 1	Sub-county	Start date	MRC 2	Sub-county	Start date
1	Agago	Patongo HCIII	Patongo TC	Aug 14	Lira-Kato HCIII	Lapono	Oct 19
2	Amuru	Atiak HCIV	Atiak	Sep 14	Amuru HCIII	Amuru	Nov 19
3	Gulu	Awach HCIV	Awach	Aug 14	Pabwo HCIII	Bungatira	Oct 19
4	Kitgum	Namokora HCIV	Namokora	Sep 14	Kitgum Matidi HCIII	Kitgum Matidi	Nov 19
5	Koboko	Lobule HCIII	Lobule	Aug 18	Ayipe HCIII	Kuluba	Dec 19
6	Kole	Aboke HCIV	Aboke	Mar 14	Bala HCIII	Bala	Nov 19
7	Lamwo	Padibe HCIII	Padibe	Sep 14	Madi-Opei HCIII	Madi-Opei	Nov 19
8	Arua	Opia HCIII	Vurra	Sep 14	Cilio HCIII	Aii-vu	Dec 19
9	Nwoya	Koch Goma HCIV	Koch Goma	May 19	Alero HCIII	Alero	Jan 20
10	Omoro	Lalogi HCIV	Lalogi	Sep 14	Bobi HCIII	Bobi	Jan 20
11	Oyam	Anyeke HCIV	Oyam TC	Apr 14	Otwal HCIII	Otwal	Nov 19
12	Amuria	Asamuk HCIII	Asamuk	Nov 19	Morungatuny HCIII	Morungatuny	Dec 19
13	Bukedea	Bukedea HCIV	Bukedea	Nov 19	Kolir HCIII	Kolir	Nov 19
14	Kumi	Kamaca HCIII	Kanyum	Jan 20	Omatenga HCIII	Kumi	Nov 19
15	Apac	Teboke HCIII	Chegere	Feb 20	Akokoro HCIII	Akokoro	Feb 20
16	Busia	Lumino HCIII	Lumino	Jun 18	Busitema HCIII	Busitema	Mar 20
17	Jinja	Budondo HCIV	Budondo	Jan 20	Butagaya HCIII	Butagaya	Jan 20

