### 8.1 Primary outcome

The primary outcome of the study will be the cumulative incidence of malaria over the 24 month follow-up period. The total number of cases of malaria for each MRC target area will be the number of laboratory confirmed cases of malaria from patients who report residing in the target area over the 24 month follow-up period, with two correction factors: 1) for patients who reside within the target area with suspected malaria who do not undergo laboratory testing, and 2) for patients with laboratory confirmed malaria whose village of residence is missing. The population of the MRC target area will be used for incidence calculations.

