### 9.3 Subgroups and exploratory analyses

#### 9.3.1 Subgroup analyses

The following subgroup analyses have been planned *a priori*:

1. Primary outcome (malaria incidence) will be stratified according to the following 3 age strata: < 15 years, 5-15 years, and over 15 years.
2. Secondary outcomes for LLIN ownership, coverage and use will be stratified according to the following 3 age strata: < 15 years, 5-15 years, and over 15 years.

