### 9.4 Missing data

For estimates of malaria incidence, adjustments will be made when calculating the number of cases of laboratory-confirmed malaria by adding estimates for the following categories of patients: 1) Malaria cases due to missing data on diagnostic testing = patients residing in the target area with suspected malaria but no laboratory test done multiplied by the test positivity rate among patients residing in the target area with suspected malaria and tested for malaria. 2) Malaria case due to missing data on location of residence = patients with laboratory confirmed malaria with missing data on village of residence multiplied by the proportion of patients with laboratory confirmed malaria who reside in the target area.

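### SAP 9.4 corrects the primary case count with an MRC-wide residence share and an unstratified test positivity rate, leaving recorded parish, age and month unused

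*Protocol*

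**What the plan says.** SAP 8.1 builds the primary case total for each MRC target area "with two correction factors: 1) for patients who reside within the target area with suspected malaria who do not undergo laboratory testing", and a second factor for confirmed cases whose village is missing. Protocol 13.3 has the same two corrections.

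SAP 9.4 gives the formulas:

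- Untested suspected residents are "multiplied by the test positivity rate among patients residing in the target area with suspected malaria and tested for malaria".
- Confirmed cases with a blank village are "multiplied by the proportion of patients with laboratory confirmed malaria who reside in the target area".

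Neither formula mentions parish, age or calendar period. On period, Protocol 1.5 says only that "the total number of malaria episodes from the MRC target area during the time of interest is calculated as the sum of the following".

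The register holds more than these formulas use. Protocol 1.5 reports that "we began collecting data on village and parish of residence for all patients presenting to the health facilities in 2017". Protocol 6.1 states that the data captured "includes location of residence (parish and village), age, gender, body temperature", among other fields; SAP 5.2 has the same list. Visit date is not in the list, but monthly data submission (SAP 5.2) and the monthly positivity and incidence plot for one MRC (Protocol Figure 7) imply that month is known.

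Protocol 13.2 and SAP 3.2 confine target-area villages to the MRC's own sub-county. SAP 9.3.1 adds that "Primary outcome (malaria incidence) will be stratified according to the following 3 age strata", without saying whether the corrections are made within stratum.

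**The concern.** Both corrections sit inside the primary numerator, so their form matters.

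**Residence.** A patient with no village but a recorded parish in another sub-county is outside the target area by the trial's own definition. The formula still credits that patient as a fractional resident case. More generally, the MRC-wide share ignores parish whenever parish is known.

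**Testing.** Positivity varies by month and may vary by age. If one rate covers 24 months or all ages, and untested patients fall in particular months or ages, the estimated positives will be off. The protocol raises the possibility: it says COVID-19 may act through "decreased availability of ACTs or rapid diagnostic tests through interruption of the supply chain". A rate pooled over 24 months would also carry the same positivity into both halves of the planned year 1 versus year 2 analysis, and an all-age rate would distort the age strata.

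At stake are absolute incidence (which also feeds cases averted in the economic evaluation), the age-specific and year-specific results, and, if the error is uneven, the precision or bias of the IRR.

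**Working it through.** **The plan's own figure.** Inputs from Protocol 13.4.1: rates 0.332 and 0.332 × 0.74 = 0.2457 per person-year, CV 0.42, 80% power, two-sided 0.05. Person-years per cluster: 1,500 × 2 = 3,000 (minimum population from Protocol 13.2). Using the Hayes-Bennett formula for unmatched rates without the extra cluster:

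c = 7.849 × [(0.332 + 0.2457)/3000 + 0.42² × (0.332² + 0.2457²)] / (0.332 − 0.2457)² = 31.9, so 32 per arm.

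This reproduces the plan (power 80.1%). With the extra cluster, 33 are needed and 32 give 78.9%. The corrections alter no input here, so the sample size itself is not in dispute.

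**Village rule.** Let m be the share of confirmed cases with no village, p the target-area share among known villages, and q the true share among blank ones. Relative count error = p / [(1 − m)p + mq] − 1. The documents give neither m nor q, so these are assumed ranges:

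| m | q = 0 | q = p/2 | q = p | q = 1.5p |
|---|---|---|---|---|
| 2% | +2.0% | +1.0% | 0 | −1.0% |
| 5% | +5.3% | +2.6% | 0 | −2.4% |
| 10% | +11.1% | +5.3% | 0 | −4.8% |
| 20% | +25.0% | +11.1% | 0 | −9.1% |

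Parish helps as follows. Write p = Σ wₖpₖ, where wₖ is the parish mix of known-village cases and pₖ the target-area share within parish k. If blank-village cases have mix vₖ and the same pₖ, the right multiplier is Σ vₖpₖ. The MRC-wide share is wrong by Σ (wₖ − vₖ)pₖ, which vanishes only when the weighted difference in mix does.

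**Test rule.** Assumed pattern: 24 months, 8 peak months with 200 suspected residents each and 16 with 100, positivity 60% peak and 40% otherwise. True cases = 8 × 200 × 0.6 + 16 × 100 × 0.4 = 1,600 among 3,200 suspected.

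- Half untested in 4 peak months: 400 untested, confirmed = 1,600 − 400 × 0.6 = 1,360, tested = 2,800. One pooled rate gives 1,360 × 3,200/2,800 = 1,554, an error of −2.9%.
- Half untested in 4 low months: 200 untested, confirmed = 1,520, tested = 3,000. The pooled rate gives 1,621, an error of +1.3%.

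Across 2 to 6 months at 50% untested, or 4 months at 80%, with positivity 40/60% or 30/70%, the error is −1.3% to −10.0% for peak months and +0.6% to +4.4% for low months. Month-specific positivity gives zero error if testing within a month is unselective.

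**Age strata.** Assume 10% untested and an all-age rate of 45% applied in every stratum. A stratum with true positivity 30% gets (0.9 × 0.30 + 0.1 × 0.45)/0.30 = 1.05, or +5.0%. One at 60% gets (0.54 + 0.045)/0.60 = 0.975, or −2.5%.

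**Effect on the IRR.** Equal error in both arms leaves 0.740. An error of +5% in the PPF arm alone gives 0.74 × 1.05 = 0.777 (power about 66%); +10% gives 0.814 (about 49%). If the miscount is random between clusters with SD s, CV becomes √(0.42² + s² + 0.42²s²). For s = 5%, 10% and 15% this is 0.424, 0.434 and 0.450, requiring 33, 35 and 37 clusters per arm, with power at 32 of 79.5%, 77.6% and 74.5%.

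**The case against.** The case for leaving the rule alone is substantial.

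- A reader might infer that positivity is pooled over 24 months. The SAP does not say so. SAP 8.1 fixes the period of the case total, not of the multiplier, and monthly corrected counts also sum to a 24-month total. Run by MRC and month, the rule largely escapes the stock-out problem. This stands: the defect is an unstated window.
- A reader might infer that blank villages belong mainly to distant patients, so the count is too high. Protocol 1.5 says only that maps of the surrounding villages were given to the MRCs. Nothing shows who lacks a village, and the error can take either sign.
- Parish and village are recorded together, and SAP 9.4 labels the category as missing location before its formula narrows to village. Parish may be blank whenever village is. Parish-first assignment would then simply return the existing share, so nothing is lost.
- Test shortages are a possibility, not a forecast. Protocol 6.1 provides buffer laboratory supplies, and positivity is already limited to target-area residents.
- Allocation is randomised within district between MRCs meant to be comparable in level of care, and baseline incidence is adjusted for. The documents show no mechanism that makes the error differ systematically by arm. Paired MRCs do differ in surveillance history (in Kwania, October 2006 against November 2019, Protocol Table 2), so uneven recording is plausible as noise.

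What remains is that the written formula sets aside recorded parish and age, and permits more than one reading on time.

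**Conclusion.** The point holds as a weakness in how the primary numerator is specified. SAP 9.4 counts fractional cases for patients whose recorded parish can place them outside the target area, and it leaves the window and age basis of the positivity rate open. The residence part needs no missingness figure to be seen in the text, though its size depends on how often parish is recorded without village. The positivity part is conditional on pooling and on untested patients clustering.

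Under the assumptions shown, errors in the count range from nil to about 10% in most scenarios; the extreme of 25% needs 20% blank villages, all of them non-residents. The documents do not support saying that the primary count is wrong, that it is wrong in a known direction, or that the IRR is biased. The IRR is biased only if the error differs by arm. Otherwise absolute incidence shifts and power may fall modestly, for example from 80.1% to 77.6% with a 10% cluster-level SD.

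**What to change.** Amend SAP 9.4 as follows:

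1. **Missing village, parish recorded:** multiply by the target-area share among known-village confirmed cases from that parish, with zero for parishes containing no target-area village. Use the MRC-wide share only when parish is also missing.
2. **Missing test:** compute positivity per MRC and calendar month. For the age-stratified analysis, compute it within age stratum as well, once the overlapping first two strata in SAP 9.3.1 are reconciled. Pool adjacent months below a pre-stated minimum number tested.
3. **Baseline covariate:** apply the same rules to the three-month baseline incidence.
4. **Reporting:** give the imputed share of cases by arm, separately for each correction, and add a sensitivity analysis restricted to confirmed, known-village cases.

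The cost is SAP wording and some programming. Parish and age are already in the register; visit month is implied and should be confirmed. The downside is sparse cells, most likely in the months with least testing, which is why the pooling threshold must be set in advance.
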